# Transcranial Continuous and Pulse Near-Infrared Light in Depression: a Placebo-Controlled Study.

## 1. Study Summary

---

**Protocol #:** 2016P001490 (MGH)/ XXX (NYUSOM)

---

**Study Purpose:** The purpose of this study is:

- To assess the antidepressant effect of the Transcranial continuous and pulse near infrared light Therapy in subjects with major depressive disorder (MDD).
- To assess the safety and tolerability of the Transcranial continuous and pulse near infrared light Therapy in MDD subjects
- To pilot test the impact on neuroinflammation of the continuous and pulse near infrared light Therapy in MDD subjects
- To pilot test the impact on cognition of the Transcranial continuous and pulse near infrared light Therapy in MDD subjects

**Trial Design:** This study includes two phases of two nearly identical clinical trials, one studying the continuous light intervention and the other studying a pulsed light intervention for the treatment of depression. The two, back-to-back clinical trials differ only for the specific treatment modality of continuous and pulse near-infrared light. Each clinical trial is a double-blind, placebo-controlled, 2-arm, sequence parallel design (SPD) study of Transcranial Light Therapy (TLT) – given in addition to current antidepressant treatments for MDD subjects.

This two-site study will randomize in its first part (**PART-1**) 24 MDD subjects (at 1:2 ratio) into 2 groups: continuous light (**c-TLT**) and sham. Sham non-responders after 6 weeks will be randomized (at a 1:1 ratio) in to c-TLT and sham. Sham responders after 6 weeks will also be randomized to ensure a chance to optimize outcome and to achieve remission at a ratio 1:1 to c-TLT and sham.

In its second part (**PART-2**), which will begin following the completion of PART-1– meaning after the first 26 randomized subjects have completed their trial, the study will randomize 26 MDD subjects (at 1:2 ratio) into 2 groups: pulse light (**p-TLT**) and sham. Sham non-responders after 6 weeks will be randomized (at a 1:1 ratio)

in to p-TLT and sham. Sham responders after 6 weeks will also be randomized to ensure a chance to optimize outcome and to achieve remission at a ratio 1:1 to p-TLT and sham.

The TLT groups in **PART- 1 and 2** will receive either one of two types of TLT treatments: c-TLT or p-TLT with identical total energy delivered per session. Two sessions per week will be delivered for the duration of each phase. In both clinical trials part 1 and part 2, the sham group (n=16) will receive 2 sham treatments per week for 6 weeks. At the end of the 6 weeks the sham will be re-randomized to TLT and sham. All subjects and investigators (except the study statistician) will be blind to treatment sequence assignment.

**Study Population:** Patients eligible for study participation will be diagnosed with major depressive disorder (MDD) by DSM (MINI) criteria. Subjects will be between 18-70 years of age (have not had 71st birthday) on the date of screening. Subjects who will be permitted into the study include those who meet all the inclusion criteria and have none of the exclusion criteria.

**Duration of Participation:** Subjects will be followed in the study for 12 weeks.

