## 4.2 Study Design

This study is a double-blind, placebo-controlled, sequenced parallel study on the use of Transcranial continuous light therapy (PART 1 – TLT-c) and pulse light therapy (PART-2 TLT-p) as treatment for depressive symptoms in patients with Major Depressive Disorder (MDD).

This study will include up to 50 subjects randomized at a 1:2 ratio into 2 groups: Transcranial Light Treatment (TLT) and sham.

All subjects will receive 2 TLT/sham treatments per week for 12 weeks. Subjects randomized to the sham group will receive sham treatments for the first 6 weeks; during weeks 7-12 subjects in the sham group will be re-randomized to either TLT or to sham. All subjects and investigators (except the study statistician) will be blind to treatment sequence assignment.

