### 5.3 Sample Size

With respect to the TLT study, we expect 100 subjects to sign informed consent, including screen failures. Assuming that 1/2 will screen fail this will lead to randomization of 50 subjects. In PART-1 (CW), we will have a n=24 with a 1st randomization 2:1 (sham:NIR), which will result in 16 subjects receiving sham and 8 subjects receiving NIR. We then assume 70% non-response to sham which leads to 11 sham subjects who are non-responders and who will undergo the 2nd randomization (week 6). Assuming a dropout rate of 24% before week 6, we anticipate that 9 subjects from the sham group will be eligible for the 2nd randomization 1:1 (sham:NIR). This 2nd randomization (week 6) will result in approximately 5 subjects receiving sham and 4 subjects receiving NIR. According to the Sequence Parallel Comparison (SPD) design the data from the 1st randomization (week 0 to 6 of the trial) and the data from the 2nd randomization (week 6 to 12 of the trial) can be pooled resulting in a total of 16+5=21 available sham subjects and 8+4=12 available NIR subjects. With this sample we have estimated >80% power to detect a significant difference ( $p \leq 0.05$ ) in depression outcome based

on the antidepressant effect size detected in our prior MGH study (ELATED-2). In PART-2 (PW) we will have an even larger power to detect a significant difference since our sample of subjects at the 1st randomization will be larger (n=26).

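### Two Study Summary sentences (the trigger of 26 for starting Part 2, and sham n=16 in both Parts) conflict with the planned Part sizes of 24 and 26

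*Protocol*

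**What the plan says.** The Trial Design paragraphs of the Protocol's Study Summary give the size of each Part. Part 1 randomizes "24 MDD subjects (at 1:2 ratio) into 2 groups: continuous light" or sham. For Part 2, "the study will randomize 26 MDD subjects (at 1:2 ratio) into 2 groups: pulse light" or sham. Part 2 is to follow completion of Part 1, which the same sentence explains as "meaning after the first 26 randomized subjects have completed their trial".

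The next paragraph of the Study Summary gives one sham size for both Parts: "In both clinical trials part 1 and part 2, the sham group (n=16) will receive 2 sham treatments per week for 6 weeks".

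Section 5.3 (Sample Size) says "In PART-1 (CW), we will have a n=24", split into 16 sham and 8 active. It puts Part 2 at 26 and says that Part 2 therefore has the greater power. On the total it says "Assuming that 1/2 will screen fail this will lead to randomization of 50 subjects". Section 4.2 sets a ceiling: "This study will include up to 50 subjects randomized at a 1:2 ratio into 2 groups". Sections 4.3.1, 4.5 and 5.1 also give 50. The SAP gives no Part sizes and no switch rule, so it does not settle the matter.

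**The concern.** The trigger is an operating rule. It decides when the study changes from continuous to pulse light, and so which modality the 25th and 26th randomized subjects can receive. A trigger of 26 cannot be applied to a Part of 24. Staff who followed the number would keep randomizing into Part 1 until 26 subjects were in it.

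The single sham figure adds a second ambiguity. If it is right for both Parts, they are equal in size and the total is not 50. If Part 2 is 26, its sham group is about 17.

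What is at stake is the size of each trial, the order of the two sizes, on which section 5.3 relies when it calls Part 2 the better powered, and the ceiling of 50. Section 4.14 has block-randomization codes pre-loaded in the devices, so the number of codes per Part has to be settled in advance.

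**Working it through.** **1. The plan's own figures (section 5.3, Part 1).**
- Sham: 24 × 2/3 = 16. Active: 24 × 1/3 = 8.
- Sham non-responders: 16 × 0.70 = 11.2, taken as 11.
- Retained to week 6: 11.2 × 0.76 = 8.5, taken as 9, split 5 sham and 4 active.
- Pooled: 16 + 5 = 21 sham and 8 + 4 = 12 active.
- Total over the Parts: 24 + 26 = 50.

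Every step reproduces. The sizes in section 5.3 equal those randomized in the Study Summary.

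**2. The same chain for a Part of 26.**
- Sham: 26 × 2/3 = 17.3. Active: 26 × 1/3 = 8.7. The nearest whole numbers are 17 and 9.
- Non-responders: 17.3 × 0.70 = 12.1. Retained: 12.1 × 0.76 = 9.2, so 9, again 5 and 4.
- Pooled: 17 + 5 = 22 sham and 9 + 4 = 13 active.

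**3. What each statement implies.**

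| Statement followed | Part 1 | Part 2 | Total |
|---|---|---|---|
| Numbers randomized in the Study Summary; section 5.3 | 24 | 26 | 50 |
| Sham n=16 in both Parts, at 1:2 | 24 | 24 | 48 |
| Trigger of 26, total held at 50 | 26 | 24 | 50 |
| Trigger of 26, Part 2 kept at 26 | 26 | 26 | 52 |

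Only the first row meets the stated Part sizes, the total of 50 and the statement that Part 2 is larger.

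**4. Effect on power.** Section 5.3 does not say which ELATED-2 effect or which sidedness it used, so both effects reported in section 3.1 (HAMD-17) are tried here, two-sided at 0.05 with normal approximation.
- Endpoint sample: difference 11.7 − 5.3 = 6.4; pooled SD √((7.5² + 7.0²)/2) = 7.25; standardized effect 0.88.
- Completers: difference 15.7 − 6.1 = 9.6; pooled SD √((5 × 4.4² + 6 × 7.9²)/11) = 6.55; standardized effect 1.47.

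Power = Φ(difference/SE − 1.96).
- Simple pooling, as in section 5.3: SE = SD × √(1/sham + 1/active).
- Equal phase weights, as in section 5.6: SE = ½ × SD × √(the sum of 1/n over the two phase-1 arms and the two phase-2 arms). This treats the two phases as independent and takes the same effect in each.

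| Method and effect | Part of 24 | Part of 26 | Change (points) |
|---|---|---|---|
| Pooled (21 vs 12; 22 vs 13), endpoint effect | 68.4% | 71.3% | 2.9 |
| Pooled, completer effect | 98.2% | 98.7% | 0.5 |
| Equal weights (16/8 and 5/4; 17/9 and 5/4), endpoint effect | 59.9% | 61.1% | 1.2 |
| Equal weights, completer effect | 95.7% | 96.1% | 0.4 |

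Without rounding the head counts, the equal-weight, endpoint-effect comparison is 58.6% against 62.0%, a change of 3.4 points. The levels depend on the assumed effect and method and are shown only to size the change. Whether the stated power above 80% is justified is a separate question.

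**The case against.** The best defence is that 26 is one wrong number in an explanatory clause. The rule being explained is completion of Part 1. The same Trial Design text puts Part 1 at 24, section 5.3 repeats it, and several sections give 50. A careful reader can recover the intent. The codes come from the statistician's list, and nothing shows that the summary clause governs its length. All of this stands. It keeps the point small and makes the total of 52 unlikely. It does not remove the contradiction: the clause is the only place where the trigger is given as a number of subjects, and that number is wrong for a Part of 24. Nor does it explain the sham size of 16 for a Part of 26.

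Three stronger readings are tempting, and the documents support none of them.

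- *The sizes behind the power statement disagree.* They do not. Section 5.3 uses 24 and 26 throughout, these match the numbers randomized in the Study Summary, and the chain reproduces.
- *The trigger requires 26 completers, hence about 34 randomized (26/0.76 = 34.2).* The phrase picks out subjects by order of randomization; it does not ask for recruitment until 26 have finished. The 76% is also retention in phase 1 only (section 5.6), not over 12 weeks.
- *The word completed contradicts the assumed 24% dropout.* It can mean that participation has ended, and section 4.8.4 encourages subjects to stay in follow-up after stopping treatment. The wording is loose, but it does not conflict with the planning assumption.

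**Conclusion.** The point holds as an internal inconsistency in current design text. Two Study Summary figures, the trigger of 26 and the sham size of 16 for Part 2, do not fit the Part sizes of 24 and 26 and the total of 50 stated elsewhere.

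Taken literally, the trigger moves two subjects (2/24, about 8% of Part 1) into continuous light. It then either reverses the order of the Part sizes or takes the total to 52.

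The statistical effect is small: about 1 to 3 points of power for a Part with the endpoint effect, and about half a point with the completer effect. These figures rest on the ELATED-2 HAMD-17 results, a two-sided 0.05 test and the normal approximation, none of which section 5.3 states as its basis. The point does not invalidate the power calculation. It is a minor correction, worth making because it settles which modality the 25th and 26th subjects receive.

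**What to change.** In the Study Summary, change the trigger to read that Part 2 starts after all 24 subjects randomized in Part 1 have completed or left the trial. The last words also remove any doubt about dropouts.

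Replace the single sham figure with planned first-randomization sizes for each Part: 8 TLT and 16 sham in Part 1; about 9 TLT and 17 sham in Part 2. The Part 2 sizes are approximate because 26 does not divide exactly at 1:2.

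Check that the randomization list pre-loaded in the devices holds code numbers consistent with 24 and 26. The cost is a wording change in the Study Summary and that check. Section 5.3, the total and the analysis need no change on this account.

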**Endpoints:**

**Safety** - The safety endpoints will evaluate the TLT and sham groups for differences in tolerability through 12 weeks of follow-up.

**Efficacy** - The efficacy endpoint will be the antidepressant effect of TLT through week 12, as assessed using the QIDS-C scale.

**Engagement of Neuro-Inflammation** – The effect of TLT on inflammation will be assessed at week 6 and 12 by measuring the plasma levels of IL6, TNF- $\alpha$ , IL-1 $\beta$  as primary cytokines (compared to baseline).

**Engagement of Cognitive circuitry** – The effect of TLT on cognition will be assessed at week 6 and 12 by measuring pattern recognition and cognition with emotional stimuli (compared to baseline).

**Entry Criteria: Inclusion Criteria**

1. Subjects age at screening will be between 18 and 70 years old (inclusive).
2. Diagnosis of major depressive disorder (MINI)
3. HAM-D17 $\geq$ 14

4. CGI-S  $\geq 4$  or higher, i.e., “moderately depressed”
5. Women of child-bearing potential must use a double-barrier method for birth control (e.g. condoms plus spermicide) if sexually active.
6. Subject Informed Consent obtained in writing in compliance with local regulations prior to enrollment into this study.
7. The subject is willing to participate in this study for at least 12 weeks.
8. Subjects will need to be on stable dose(s) of antidepressants (if taking any) for at least six weeks prior to enrollment.

**Exclusion Criteria:**

1. The subject is pregnant or lactating.
2. The subject failed more than 2 adequate treatment with FDA-approved antidepressants during current episode per ATRQ criteria (less than 50% decrease in depressive symptomatology).
3. Structured psychotherapy focused on treating the subject’s depression (i.e. CBT or IPT) is permitted if started at least 8 weeks prior to the screening visit.
4. Substance dependence or abuse in the past 3 months.
5. History of a psychotic disorder or psychotic episode (current psychotic episode per MINI assessment).
6. Bipolar affective disorder (per MINI assessment).
7. Unstable medical illness, defined as any medical illness which is not well-controlled with standard-of-care medications (e.g., insulin for diabetes mellitus, HCTZ for hypertension).
8. Active suicidal or homicidal ideation (both intention and plan are present), as determined by C-SSRS screening.
9. Cognitive impairment (MOCA < 21)
10. The subject has a significant skin condition (i.e., hemangioma, scleroderma, psoriasis, rash, open wound or tattoo) on the subject’s scalp that is found to be in proximity to any of the procedure sites.
11. The subject has an implant of any kind in the head (e.g. stent, clipped aneurysm, embolised AVM, implantable shunt – Hakim valve).
12. Any use of light-activated drugs (photodynamic therapy) within 14 days prior to study enrollment (in US: Visudine (verteporfin) – for age related macular degeneration; Aminolevulinic Acid- for actinic keratoses; Photofrin (porfimer sodium) – for esophageal cancer, non-small cell lung cancer; Levulan Kerastick (aminolevulinic acid HCl) – for actinic keratosis; 5-aminolevulinic acid (ALA)- for non-melanoma skin cancer)
13. Recent history of stroke (90 days).

14. The subject failed a device-based intervention FDA-approved for the treatment of depression, during the current episode (e.g. less than 50% decrease in depressive symptomatology with TMS, ECT or VNS).

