##### Screening Visit (Week -1)

The Principal Investigator (PI) at the site or a Sub-investigator will assess patients against the inclusion and exclusion criteria. If a patient appears to qualify and agrees to participate in the study, then the patient will undergo the informed consent process prior to initiation of any study-specific activities. Screening Case Report Forms (CRFs) will be completed and subjects who qualify to participate in the study will proceed to the first Treatment Visit 1. If the subject does not meet entry criteria, the Investigator will document the subject's ineligibility for study participation and complete the appropriate CRFs.

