##### Treatment Visits – Visits 1-24 (Weeks 1-12)

There are 2 treatment visits per week for 12 weeks. This visit-schedule applies both to the PART-1 (TLT-c) and PART-2 (TLT-p) phase of the study. Treatment Visit 1 will consist of all subjects being randomized to the TLT and Sham groups and undergoing baseline assessments including HAM-D-17, QIDS-C, ASQ and cognitive tasks prior to treatment.

Treatment Visits 1-12 will include various assessments as detailed in Section 4.8 and in Attachment 1.

##### Follow-Up Visit – Visit 25

All subjects will undergo subject assessments including HAM-D-17, QIDS-C, ASQ, and cognitive tasks at follow-up Visit 25 (Week 13).

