#### **4.17.2 Safety Monitoring**

The study subjects will undergo frequent clinical evaluations including depressive scores, concomitant medications, adverse events, and serious adverse events and unexpected device events will be recorded from study entry through completion. Additionally, doctors must monitor a subject's safety by asking the subjects frequently about the subject's own comfort during treatment application.

If skin erythema is present, treatment will be suspended. Patients will be instructed to contact the study site principal investigator or a member of his staff at any time between visits concerning adverse events or worsening of symptoms. If at any study visit the subjects' clinical condition is significantly worsened from baseline (operationalized as the clinical global impression severity score, CGI-S, of 6 or higher) or if a subject becomes actively suicidal with intent and/or plan, based on the C-SSRS scale and/or the clinical interview, the subject will be offered to start an antidepressant medication. If the subject were deemed at imminent danger as a result of suicidality, s/he would be discontinued from the study and referred to appropriate clinical treatment (see 4.8.4 Termination).

The two site Principal Investigators (Drs. [name] and [name]) will have bi-weekly conference calls (which will include study RAs); during these conference calls they will discuss all Adverse Event reports to identify any safety concern, based on such concerns they will be able to decide temporary discontinuation of study enrollment, modifications of the study protocol, or to terminate the study.

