Risk of Worsening of Depression, Suicidality & Manic Switch: Worsening of depression and increased suicidality are possible complications of antidepressant treatments prescribed to subjects with MDD. We will minimize this risk by selecting only subjects who do not present active suicidal ideation at screening. We will also discontinue any subject who develops active suicidal ideation during the course of the study (C-SSRS) and is deemed at imminent danger; we will then arrange for appropriate levels of care and standard antidepressant treatment (see 4.8.4 Termination). Manic switches are possible adverse events and will be closely monitored during antidepressant treatment as well. Our tight schedule of clinical study visits will allow early recognition of treatment-emergent suicidal ideation or prodromal hypomanic signs. Subjects who develop mania or hypomania will be discontinued and provided appropriate level of care.

Answering detailed questionnaires may create a mild degree of inconvenience for the subjects.

Length of testing for cognitive circuitry:

The total length of this task takes a total of 40 minutes at baseline and 40 minutes at week 3, 6, 9 and 12. There is no expected risk to the patients beyond the 40 minutes of sitting in front of computer for testing and possible experience of startle. Every effort will be made to ensure that the patients are comfortable and safe during this period, and the study can be stopped at any time. Beyond these issues, there is minimal or no risk to the patients.

Risk of Bruising

Venipuncture might result in accidental bruising at the sight of blood drawing on the forearms.

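### Exclusion 8 bars suicidality only when intention and plan are both present, so a subject with one alone can be randomised, and the Visit 1 C-SSRS carries no eligibility rule

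*Protocol*

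**What the plan says.** **Entry.** Exclusion 8 in the Protocol's Study Summary bars "Active suicidal or homicidal ideation (both intention and plan are present), as determined by C-SSRS screening". No other inclusion or exclusion criterion deals with suicidality.

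**Risk statement.** On worsening depression and suicidality, section 4.20.1 says: "We will minimize this risk by selecting only subjects who do not present active suicidal ideation at screening". This sentence does not mention intent or plan.

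**On-study action.** Section 4.17.2 sets a trigger that applies at any study visit: "if a subject becomes actively suicidal with intent and/or plan, based on the C-SSRS scale and/or the clinical interview". The consequence is that "the subject will be offered to start an antidepressant medication". Removal is reserved for a more serious state: "If the subject were deemed at imminent danger as a result of suicidality, s/he would be discontinued from the study". Section 4.8.4 likewise ties termination to imminent danger.

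**Path to randomisation.** Section 4.8.1 places the C-SSRS at screening and has the investigator go back over all entry criteria once the screening results are in. Section 4.7 then says "subjects who qualify to participate in the study will proceed to the first Treatment Visit 1", and that "Treatment Visit 1 will consist of all subjects being randomized to the TLT and Sham groups and undergoing baseline assessments". Section 4.8.2.1 lists the Visit 1 C-SSRS among measures taken before treatment as baseline values. Section 4.8.1 also lets a subject taper off an antidepressant before the baseline visit.

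The SAP does not address eligibility or suicidality.

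**The concern.** The entry rule is looser than the protocol's own threshold for clinical action. A subject with suicidal intent but no plan, or a plan but no stated intent, passes exclusion 8. Once on study, the same clinical state calls for an offer of medication under section 4.17.2. The risk section also presents selection at screening as the means of reducing this risk, and the criterion that sites will apply may deliver less than that sentence suggests.

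The second part concerns timing. Randomisation takes place at Visit 1, after an interval in which a subject may be coming off an antidepressant. A C-SSRS is scheduled at that visit, but nothing says that its result can stop randomisation.

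What is at stake is participant safety in a sham-controlled trial. Sample size, power and type I error are not affected.

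**Working it through.** No arithmetic decides this point. The check sets the rules side by side.

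**Step 1: the possible states.** Section 4.9 lists plan and intent among the things the C-SSRS tracks, so the instrument already gathers what is needed to tell these states apart.

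| State at assessment | Exclusion 8 | Section 4.17.2 trigger, on study |
|---|---|---|
| Intent and plan | Excluded | Antidepressant offered |
| Intent only | Not excluded | Antidepressant offered |
| Plan only | Not excluded | Antidepressant offered |
| Active ideation, neither intent nor plan | Not excluded | Not triggered |

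The second and third rows are the gap: eligible at entry, yet in a state that the protocol treats as needing action.

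**Step 2: does section 4.20.1 close it?** Read literally, that section would keep out all four rows. It is a risk description, however, and not an eligibility criterion. Sites apply exclusion 8.

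**Step 3: does Visit 1 close it?**
- The re-check of criteria in section 4.8.1 is part of the screening procedures and applies the same exclusion 8.
- Section 4.8.2.1 requires the Visit 1 C-SSRS before treatment. It does not require it before randomisation and attaches no threshold to it.
- The QIDS-C covers suicidal ideation, and the SAFTEE-SI probes suicidal thoughts and behaviour (section 4.9). Both are also done at Visit 1, and neither carries an eligibility rule.
- The Table of Assessments adds no rule.

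**Step 4: what limits the exposure?**
- Light therapy or sham is given on top of current antidepressant treatment (Study Summary, Trial Design), although a subject may choose to taper.
- The C-SSRS is scheduled at V0, at V1, at the eleven odd-numbered visits from V3 to V23, and at V25: 1 + 1 + 11 + 1 = 14 times, about weekly. Six of these fall in weeks 1 to 6 (V1, V3, V5, V7, V9, V11).
- Section 4.17.2 offers an antidepressant, and section 4.8.3 lets a subject start or change one at any time for severe worsening.
- Imminent danger leads to removal (sections 4.8.4, 4.17.2 and 4.20.1), and the investigator may end participation at any time (section 4.19.1).

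These measures manage a subject or leave the decision to judgement. None makes intent alone or a plan alone a reason not to randomise.

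**The case against.** The strongest reply is that the two thresholds do different jobs. An offer of medication can reasonably be triggered at a lower level than exclusion from a trial. Section 4.17.2 also speaks of a subject who becomes suicidal, which points to change during the study. Its other trigger, worsening "operationalized as the clinical global impression severity score, CGI-S, of 6 or higher", has no matching ceiling at entry, since inclusion 4 sets only a minimum CGI-S of 4. The on-study triggers were evidently not written as a mirror of the entry criteria. This stands: the difference may be deliberate, and it is not in itself an error.

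A reader might also infer that exclusion 8 and section 4.20.1 flatly contradict each other. The documents do not support that firmly. Exclusion 8 uses the term active suicidal ideation and explains it in brackets, and section 4.20.1 may simply repeat the term in short form. The conflict is then one of wording. The gap for intent alone or a plan alone remains on either reading.

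A third reply is that Visit 1 is already protected. The section 4.17.2 trigger applies there, the investigator may withdraw a subject, and the reference to C-SSRS screening in exclusion 8 could mean the instrument and not the visit. It would also be wrong to infer that the C-SSRS is the only Visit 1 measure to pick up suicidality after screening, because the QIDS-C and SAFTEE-SI do so too. What survives is narrower: none of these measures is tied to the decision to randomise.

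**Conclusion.** The point holds as a cheap safety improvement. As written, exclusion 8 lets a subject with suicidal intent alone or a plan alone be randomised, and no stated rule stops randomisation if either emerges between screening and Visit 1. This rests on a literal reading of exclusion 8 and on the absence of any eligibility rule in section 4.8.2.1 or the Table of Assessments.

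The number of subjects affected cannot be computed: the documents give no prevalence of these states, and none is assumed here. A reader might take the share of subjects allocated to sham as a measure of the risk. It is not, because it describes the allocation of every randomised subject and not how many enter through this gap. Nor does sham allocation in itself withhold standard treatment in an add-on design. No bias in the endpoint is claimed.

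**What to change.** 1. Reword the suicidality part of exclusion 8: *Active suicidal ideation with intention and/or plan, as determined by C-SSRS and/or clinical interview.*
2. Keep the homicidal-ideation exclusion as a separate clause with its present threshold, so that the edit does not delete it.
3. Add one line to section 4.8.2.1: the Visit 1 C-SSRS is scored, and exclusion 8 applied to it, before the randomisation code is matched to the study ID under section 4.14. The criterion then applies at both V0 and V1.
4. Leave sections 4.8.4, 4.17.2 and 4.20.1 as they are.

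The cost is one line in exclusion 8 and one in section 4.8.2.1. No new assessment is needed, because the C-SSRS is already scheduled at both visits. The downside is possibly a few more screen failures, some found only at Visit 1.

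The edit does not fully match a literal reading of section 4.20.1: active ideation with neither intent nor plan would still pass exclusion 8. If the sponsor means that section literally, exclusion 8 would have to cover any active suicidal ideation.
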